- Post-therapy outcomes: increased O₂ requirement (PaO₂/FiO₂ ratio or SpO₂/FiO₂), supplemental oxygen strategy (e.g. nasal cannula, high-flow nasal cannula, noninvasive ventilation, intubation and invasive mechanical ventilation, rescue ventilation i.e. neuromuscular blocking agents, prone positioning, corticosteroids, ECMO), vasopressors, renal support, ICU LOS, ICU mortality, Hospital LOS, Hospital mortality, 28 day mortality.

Study Agent:

- SARS-CoV-2 convalescent plasma (1 unit, on average ~300 mLs)

Primary Objective/Outcome:

1. Feasibility of performing study pathway consisting of consenting convalescent donors, harvesting convalescent plasma, application for FDA eIND and administering convalescent plasma to the patients
 - a. Feasibility will be defined as 6-7 recipient subjects out of a total proposed number of 10 recipient subjects will complete the study infusion of plasma and be evaluable for follow-up with at least 24 hours' worth of data post transfusion. Post-transfusion data will include assessment of the study process, outcome endpoints and safety endpoints.
2. Type and duration of respiratory support (e.g. CPAP, BiPAP, high-flow nasal cannula, mechanical ventilation)

Primary Endpoint: Number of patients meeting inclusion criteria who received anti-SARS-CoV-2 convalescent plasma in the study period

Secondary endpoints:

1. Cardio-circulatory arrest (at any time)
2. Transfer to ICU
3. ICU mortality and LOS
4. Hospital mortality and LOS
5. Ventilator-free days
6. 28 day mortality

Primary Safety Objective: Evaluate the safety of an investigational treatment with anti-SARS-CoV-2 plasma in hospitalized patients with severe or life-threatening COVID-19

Primary Safety Endpoints:

1. Rapid deterioration of respiratory or clinical status during transfusion of anti-SARS-CoV-2 convalescent plasma
2. Cumulative incidence of serious adverse events during the study period: transfusion reaction (fever, rash), transfusion related acute lung injury (TRALI),

transfusion associated circulatory overload (TACO), transfusion related infection, new acute respiratory distress syndrome (ARDS).

Secondary Objectives:

1. Measure rates, levels and duration of SARS-CoV-2 RNA in nasopharyngeal swabs using RT-PCR among recipients. Other specimen types may be tested as available (e.g., BAL fluid, tracheal secretions, sputum, etc.) or when RT-PCR assays are validated for additional sources (i.e., stool, blood).

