Biomarker tests performed in the research lab include antibody titer, neutralizing antibody, cytokine levels, viremia

¹ The assessments performed on day 28 will be repeated on days 60 and 90.

² Vital sign testing: Immediately prior to infusion, 10-20 minutes after start of infusion, at completion of infusion and 30-60 minutes after the end of the infusion

Subject Withdrawal

- Subjects can terminate study participation and/or withdraw consent at any time without prejudice.
- Subjects who withdraw from the study will not be replaced.
- The investigator may withdraw subjects if they are lost to follow up, non-compliant with study procedures or if the investigator determines that continued participation in the study would be harmful to the subject or the integrity of the study data.
- Discontinuation of the study: The IRB has the right to terminate this study at any time

Investigational plasmaTreatment

- Recipient subjects will receive anti-SARS-CoV-2 convalescent plasma as a pilot study after approval of single patient eIND application.
- Recipient subjects will receive anti-SARS-CoV-2 convalescent plasma under IRB20-0825
- Investigational Product: The investigational product is anti-SARS-CoV-2 convalescent plasma obtained from donors identified as having recovered from COVID-19.
- Donors samples will have been screened for transfusion-transmitted infections (e.g. HIV, HBV, HCV, WNV, HTLV-I/II, *T.cruzi*, syphilis, ZIKV) both through the use of the UCM Blood Donation Center Blood Donation Record and FDA-mandated blood donor screening tests. Plasma will have been collected as whole blood derived units donations and in accordance with standard FDA and blood bank protocols. Plasma will be ABO-compatible and HLA-screened per standard FDA and blood bank protocols.
- Recipient subjects will receive 1 unit of convalescent plasma after eIND approval. When CLIA clinical testing for antibody is available, plasma will be transfused with an anti-SARS-CoV-2 titer of >1:320, though this titer may be adjusted as *in vitro* titer assays of virus neutralization are correlated with *in vivo* assessments of virus neutralization.
- Plasma will be labeled according to FDA and blood bank guidelines.

Research biomarkers and other studies

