- If an AE develops during infusion, the infusion may be slowed or stopped as per investigator's decision.
 - Most reactions to plasma are relatively minor and the infusion can generally be continued. Infusion site burning and non-allergic systemic effects can generally be managed with slowing of the infusion. Infusion can generally be continued in cases of itching or hives after pausing the transfusion, administering antihistamines, and observing the patient for worsening.
 - Severe allergic reactions such as, bronchospasm and hypotension, and may require discontinuation of the infusion.

Concomitant medications will be documented on the CRF

- Prescription medications
- Over the counter medications

- Herbal treatments/nutritional supplements
- Blood products

Statistical considerations

Statistical Analysis

This is a pilot study focused on determining the protocol feasibility with limited subject enrollment. Therefore, statistical analysis will include descriptive summaries of both the primary and secondary outcomes of interest. For continuous variables we will determine: median, minimum and maximum values. Categorical variables will be summarized by the frequency. Unless otherwise indicated, percentages in tables will be column percentages, using the total number of observations in the population ($n=10$), as the denominator. Percentages will be rounded to one decimal place, and thus may not always add up to exactly 100%. Clinical laboratory values will be first reported in using International System of Units (SI).

Analysis of AE data

Analysis of AE data will primarily be descriptive based on MedDRA coding of events. The proportion of subjects experiencing an SAE and the proportion experiencing a Grade 3 or higher AE will be measured.

Analysis of SARS-CoV-2 viremia

Analysis of SARS-CoV-2 viremia will primarily be descriptive, comparing the viremia levels at days 0,1,3,7 and 14 between the subject recipients.

Analysis of research biomarkers

Analysis of biomarker tests performed in the research lab such as antibody titers, cytokine levels will primarily be descriptive, comparing the titers at days 0,1,3,7 and 14 between subject recipients.

Endpoints

Primary Endpoint:

1. Feasibility of performing study pathway consisting of consenting convalescent donors, harvesting convalescent plasma, application for FDA eIND and administering convalescent plasma to the patients

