Study data are accessible at all times for the team to review, and to the Independent Safety Monitor upon request. The PIs and co-investigators review study conduct, particularly accrual, drop-outs, and protocol deviations on a quarterly basis. The team reviews adverse events (AEs) individually in real-time and in aggregate on a quarterly basis. The PIs review serious adverse events (SAEs) in real-time. The PIs ensure that all protocol deviations, AEs and SAEs are reported to the IRB according to the applicable regulatory requirements.

1. Safety Evaluations will assess for the safety of anti-SARS-CoV-2 plasma
2. Clinical evaluations: Vital signs and symptom screen on days 0-7, 14 and symptom screens on days 28, 60, and 90.
3. Laboratory evaluations consistent with ongoing medical care may include radiographic imaging modalities such as chest x-rays and chest CT.
4. Safety laboratory tests (ABO typing, pregnancy testing, CBC, CRP, and comprehensive metabolic panel) will be performed at the local CLIA-certified clinical laboratory on days 0-7 and 14.

Event (AE)

Any untoward medical occurrence in a clinical investigation subject who has received a study intervention and that does not necessarily have to have a causal relationship with the study product. An AE can, therefore, be any unfavorable and unintended sign (including an abnormal laboratory finding, for example), symptom, or disease temporally associated with the use of the study product, whether or not considered related to the study product.

Serious Adverse Event (SAE)

An SAE is any adverse event that results in any of the following outcomes:

1. Death
2. Life-threatening (immediate risk of death)
3. Prolongation of existing hospitalization
4. Persistent or significant disability or incapacity
5. Important medical events that may not result in death, be life threatening, or require intervention or escalation of care may be considered a serious adverse event when, based upon appropriate medical judgment, they may jeopardize the subject and may require medical or surgical intervention to prevent one of the outcomes listed in this definition. Examples of such medical events include allergic bronchospasm requiring intensive treatment in an emergency room or at home, blood dyscrasias or convulsions that do not result in inpatient hospitalization.

Unexpected Adverse event: (UAE) An adverse reaction, the nature or severity of which is not consistent with the investigator's brochure.

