At any time after completion of the study, if the investigator becomes aware of a SAE that is suspected to be related to study product, this will be reported.

Collection and reporting of SAEs and AEs. Documentation of adverse events will be determined by the clinician and recorded on the Clinical Adverse Event Report form and will include the following information: Description of the condition, dates of condition, treatment of condition (medications, doses, dates), whether emergency treatment was required, treatment outcome, relationship of the adverse event to the study medication(s) and severity of the event. Additional information about the AE will be provided as needed so as to understand the scope of the event.

Management of SAEs. Serious adverse events are always managed, first and foremost, based on medical appropriateness so as to ensure subject safety. The PIs are notified as soon as possible about an SAE and will work with the medical team to ensure the best resolution possible of the problem. In medical emergencies the PIs are permitted to provide all health-care providers with appropriate medical information at hand about the subject consistent with HIPAA regulations.

Serious adverse events will be forwarded by the PI to the Independent Safety Monitor and IRB immediately. Fatal or life-threatening unexpected SAEs will be reported to the

IRB immediately. Non-fatal, non-life-threatening unexpected SAEs will be reported to the Independent Safety Monitor within 72 hours.

Investigator's Assessment of Adverse Events

The determination of seriousness, severity, and causality will be made by an on-site investigator who is qualified (licensed) to diagnose adverse event information, provide a medical evaluation of adverse events, and classify adverse events based upon medical judgment. This includes but is not limited to physicians, physician assistants, and nurse practitioners.

Laboratory abnormalities will be reported as AEs if there is a 2 s.d. increase above baseline.

Assessment of Seriousness

1. Event seriousness will be determined according to the protocol definition of an SAE
2. Assessment of Severity

Event severity will be assigned according to the scale below

- 1 = Mild: Transient or mild discomfort (<48 hours); no medical intervention/therapy required.)
- 2 = Moderate: Some worsening of symptoms but no or minimal medical intervention/therapy required)
- 3 = Severe: Escalation of medical intervention/therapy required

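### The SAE definition omits new inpatient hospitalization, so whether a readmission after discharge counts as serious is largely left to the investigator's discretion

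*Combined protocol and SAP*

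**What the plan says.** The section Serious Adverse Event (SAE) opens with "An SAE is any adverse event that results in any of the following outcomes" and lists five items: death, life threat, "Prolongation of existing hospitalization", lasting or significant disability, and other medically important events. The fifth item is a matter of judgment. Such events "may be considered a serious adverse event when, based upon appropriate medical judgment, they may jeopardize the subject" and may need intervention to prevent a listed outcome. Its examples end with "blood dyscrasias or convulsions that do not result in inpatient hospitalization".

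The list governs classification. Under Assessment of Seriousness, "Event seriousness will be determined according to the protocol definition of an SAE".

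Recipients are inpatients at enrollment, but follow-up is not confined to that stay. Day 28 is described as a telephone follow-up, and Table 2, footnote 1, says "The assessments performed on day 28 will be repeated on days 60 and 90". AE evaluation is scheduled at all three contacts.

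SAE status then feeds several parts of the plan:
- Analysis of AE data: "The proportion of subjects experiencing an SAE and the proportion experiencing a Grade 3 or higher AE will be measured". The general rule under Statistical Analysis sets the denominator at 10.
- Endpoints and Protocol Summary: the second primary safety endpoint begins "Cumulative incidence of serious adverse events during the study period: transfusion reaction (fever, rash), transfusion related acute lung injury (TRALI" and goes on to name further transfusion events. The Protocol Summary version adds new ARDS; the Endpoints version does not.
- Management of SAEs and Safety Oversight: SAEs go to the Independent Safety Monitor and the IRB, and the monitor writes an assessment of each.
- Halting Criteria for the Study, item 3: a single SAE attributed to the study product stops enrollment and dosing pending review.

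**The concern.** Once a recipient has gone home there is no current stay to prolong, so item 3 cannot apply to a later admission. No other section adds new hospitalization as a criterion. The fifth item's example also singles out events that do not lead to admission, a qualifier that is needed only if events leading to admission are already serious. The omission therefore looks like a drafting slip rather than a decision.

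At stake is consistent classification. Two qualified investigators could follow the text and class the same readmission differently. If it is classed as non-serious, the subject may be missing from the SAE proportion. The event is still reviewed by the study team, but under Monitoring procedures the Independent Safety Monitor sees study data only on request. Halting item 3 is not met even if the event is attributed to the plasma. The error runs in one direction: the treatment looks safer than it was.

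**Working it through.** The plan states no SAE rate, readmission rate or precision target, so there is no figure of its own to reproduce. The check is textual, followed by an illustration of scale.

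**1. A readmission against the five items.**
- Items 1, 2 and 4: met if the event is fatal, life-threatening or disabling.
- Item 3: not met after discharge.
- Item 5: possible, but permissive, and framed around events that may not need escalation of care, whereas a readmission is itself an escalation.

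A readmission outside items 1, 2 and 4 is therefore serious only if the investigator chooses to use item 5.

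**2. Is it collected anyway?** The Day 28 contact lists being in hospital as a status item. That gives the position on the day and would not show an admission that began and ended between contacts. The AE evaluation should pick up the underlying event as an AE. However, the fields named under Collection and reporting of SAEs and AEs include emergency treatment but not hospitalization.

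**3. Reporting window.** Under Definitions, a subject counts as completed at Day 90, or earlier if an adverse event or death has occurred. Under Reporting Interval, AE and SAE documentation runs until completion. Read literally, a first AE could close documentation before a later readmission.

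**4. Effect of one unclassified event.** Input: n = 10 (Statistical Analysis). One subject is 1/10 = 10.0 percentage points. Exact (Clopper-Pearson) 95% limits:
- 1/10: 0.3% to 44.5%
- 0/10: 0% to 30.8%, where the upper limit is 1 − 0.025^(1/10) = 0.308

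The proportion counts subjects, so it moves only if that subject had no other SAE.

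**5. How likely is such an event?** Everything here is assumed: 7 of 10 recipients discharged alive, a readmission probability p of 10% or 20% by Day 90, and independence between subjects.
- Expected readmissions: 7 × 0.10 = 0.7 to 7 × 0.20 = 1.4
- P(at least one readmission) = 1 − (1 − p)^7: 1 − 0.9^7 = 52.2%; 1 − 0.8^7 = 79.0%

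If a share c of readmissions is classed as serious under the other items, P(at least one missed) = 1 − (1 − p(1 − c))^7:

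| Share captured, c (assumed) | p = 10% | p = 20% |
|---|---|---|
| 0 | 52.2% | 79.0% |
| 50% | 30.2% | 52.2% |
| 80% | 13.2% | 24.9% |

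The first row is the upper bound for each p, since it requires every readmission to be missed.

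**The case against.** The strongest reply is that little is lost. The gravest readmissions are serious under items 1, 2 and 4. Item 5 asks only that intervention may be needed to prevent a listed outcome; admission itself need not be listed. Its examples are milder than an admission, so a sensible investigator would hardly rate an admission for the same problem lower. A readmission classed as non-serious is still an AE, can be Grade 3 because that grade rests on escalation of care, and then enters the Grade 3 or higher proportion. Halting item 6 covers any event the physician judges serious. This is also a descriptive pilot of 10 recipients with no threshold on the SAE rate.

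Much of this stands. A reader might infer that readmissions disappear from the safety data. The documents do not support that: the routes above remain open, and what is lost is a fixed rule. A reader might also infer that the primary safety endpoint is necessarily under-counted. That does not follow either. If the transfusion events named after the colon are exhaustive, a readmission for any other cause lies outside that endpoint however an SAE is defined. If they are examples, the gap carries through. The documents do not say which, and the two versions of the list differ.

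The reply does not remove the defect. Item 5 and halting item 6 both rest on judgment, the Grade 3 or higher proportion is a separate summary, and SAE status is what triggers prompt reporting to the monitor and IRB. It is also no answer that recipients are already inpatients, because the plan follows them after they leave.

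**Conclusion.** The definition is wrong as written and at odds with its own example. A readmission that is not fatal, life-threatening or disabling is serious only by discretion. The consequences that the text supports are a possible under-count in the proportion of subjects with an SAE, and possible failure to trigger prompt monitor and IRB reporting and the associated-SAE halting item.

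The effect on the proportion is 10.0 percentage points per subject affected, provided that subject has no other SAE. In severely ill patients that proviso may often fail. The 52–79% is the chance of at least one readmission under assumed discharge and readmission figures. It should not be read as the chance of a missed SAE, which is lower to the extent that other items capture the event.

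This should be corrected, but it ranks below defects that would undermine the pilot: the analysis is descriptive, feasibility is the main aim, and no decision threshold rests on the SAE rate.

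**What to change.** - Extend item 3 of the SAE definition to cover inpatient hospitalization, including readmission after discharge, alongside prolongation of a current stay.
- At the Day 28, 60 and 90 contacts, record any readmission since the previous contact, with dates and reason, rather than only where the subject is that day.
- Reconcile Definitions (an adverse event before Day 90 counts as completion) with Reporting Interval (documentation ends at completion), so that SAEs are recorded through Day 90. Without this, rewording item 3 would not secure capture.
- State whether the events named in the second primary safety endpoint are exhaustive or examples, and align the Protocol Summary and Endpoints versions.

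The cost is a few words in the protocol and one question at contacts already scheduled. The reported SAE rate may be slightly higher, and some additional events may go to the monitor and IRB.

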 - Medical history (timing of exposure to COVID-19 source patient, acute and chronic medical condition, medications, allergies, any drug trial therapy. Any medical condition arising after consent should be recorded as AE)
 - COVID-19 symptom screen (fevers, cough, shortness of breath), day of onset of symptoms
 - Vital signs
 - COVID-19 testing (RT-PCR) from nasopharyngeal, throat, blood or stool (optional) samples. Other clinically-approved SARS-CoV-2 testing may be used if available (e.g. saliva, nares, blood).
 - Blood typing, CBC, comprehensive metabolic panel
 - Urine or serum pregnancy test for females of childbearing potential. Results from laboratory tests obtained up to 7 days before enrollment may be used for the pregnancy test.
 - Stored samples for biomarker tests performed in the research lab (e.g. antibody titer, cytokines)
 - Determination of eligibility as per inclusion/exclusion criteria
4. Application and approval of eIND per FDA guidelines for single patient compassionate use of convalescent plasma

DAY 0:

1. Study Plasma Administration: 1 unit of plasma will be transfused. Time at start and end of infusion will be recorded and Vital signs will be measured immediately prior to infusion, 10-20 minutes after start of infusion, at completion of infusion and 30-60 minutes after the end of the infusion
2. COVID-19 symptom screen (fevers, cough, shortness of breath)
3. Assessment of clinical status (7-point ordinal scale)
4. New medical conditions, concomitant medication, AE evaluation
5. physical examination
6. Blood typing, CBC, comprehensive metabolic panel, C-reactive protein
7. Stored samples for biomarker tests performed in the research lab (e.g. antibody titer, cytokines)

Day 1-7 (or for duration of hospitalization)

1. Vital signs daily
2. COVID-19 symptom screen (fevers, cough, shortness of breath)
3. Assessment of clinical status (7-point ordinal scale)
4. New medical conditions, AE evaluation
5. physical examination
6. CBC, comprehensive metabolic panel, CRP daily
7. COVID-19 testing (RT-PCR) from nasopharyngeal, throat, blood or stool (optional) samples. Other clinically-approved SARS-CoV-2 testing may be used if available (e.g. saliva, nares, blood)

8. Stored samples for biomarker tests performed in the research lab (e.g. antibody titer, cytokines)

Day 28:

Key issues to consider follow up by phone, alive, at home, in hospital (ICU or not), on supplemental O2 or not, back to work, fully, partially, SNF, nursing home, LTAC

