The study enrollment and dosing will be stopped and an ad hoc review will be performed if any of the specific following events occur or, if in the judgment of the study physician, subject safety is at risk of being compromised:

1. Death within one hour of plasma infusion
2. Occurrence of a life-threatening allergic/hypersensitivity reaction (anaphylaxis), manifested by bronchospasm with or without urticaria or angioedema requiring hemodynamic support with pressor medications or mechanical ventilation. , TRALI, TACO
3. One subject with an SAE associated with study product.
4. Two subjects with a Grade 3 or higher lab toxicity for the same parameter associated with study product.
5. An overall pattern of symptomatic, clinical, or laboratory events that the medical monitor, ISM, or SMC consider associated with study product and that may appear minor in terms of individual events but that collectively may represent a serious potential concern for safety.
6. Any other event(s) which is considered to be a serious adverse event in the good clinical judgment of the responsible physician. This will be appropriately documented.

Upon completion of this review and receipt of the advice of the ISM, the IRB will determine if study entry or study dosing should be interrupted or if study entry and study dosing may continue according to the protocol.

Halting Criteria/Rules for Subject Infusion

Infusion of study drug will be halted if any of the following manifestations of anaphylaxis develop and will not be restarted:

- Skin or mucous membrane manifestations: hives, pruritus, flushing, swollen lips, tongue or uvula
- Respiratory compromise: dyspnea, wheezing, stridor, hypoxemia
- A decrease in systolic blood pressure to < 90 mmHg or >30% decrease from baseline or a diastolic drop of >30% from baseline.

- Tachycardia with an increase in resting heart rate to > 130bpm; or bradycardia <40 that is associated with dizziness, nausea or feeling faint.
- Any other symptom or sign which in the good clinical judgment of the study clinician or supervising physician warrants halting the infusion. For example, the rapid onset of gastrointestinal symptoms, such as nausea, vomiting, diarrhea, and cramps, for instance, may be manifestations of anaphylaxis and may warrant an immediate halt prior to meeting full SAE criteria

Ethics/Protection of human subjects

Ethical Standard

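### The only numerical laboratory AE trigger covers rises alone and rests on an undefined s.d. and baseline, so falls have no trigger and laboratory AE counts are not reproducible

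*Combined protocol and SAP*

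**What the plan says.** The laboratory rule is one sentence under Investigator's Assessment of Adverse Events: "Laboratory abnormalities will be reported as AEs if there is a 2 s.d. increase above baseline". It does not say what the s.d. is an s.d. of, or which value is the baseline.

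Other sections bear on it:

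- **General AE definition** (Safety measures, Event (AE)): an AE can be "any unfavorable and unintended sign (including an abnormal laboratory finding, for example". No direction is stated.
- **Who decides** (Collection and reporting of SAEs and AEs): "Documentation of adverse events will be determined by the clinician".
- **What is measured** (Safety measures): "Safety laboratory tests (ABO typing, pregnancy testing, CBC, CRP, and comprehensive metabolic panel) will be performed" on days 0 to 7 and 14. The recipient procedures for days 1 to 7 list "CBC, comprehensive metabolic panel, CRP daily". Table 2 has the blood count and metabolic panel after baseline on days 1, 3, 7 and 14 only.
- **Analysis** (Statistical considerations): continuous variables get a median, minimum and maximum. AE output is the proportion with an SAE and the proportion with a Grade 3 or higher AE, with percentages taken "using the total number of observations in the population ($n=10$), as the denominator".
- **Study halting**, item 4: "Two subjects with a Grade 3 or higher lab toxicity for the same parameter associated with study product".
- **Severity scale** (Assessment of Severity): five levels defined by discomfort, symptoms, how far treatment must be escalated, and death. No level carries a laboratory limit.

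**The concern.** For several analytes in a blood count the harmful direction is down, and the Study Design summary itself lists neutrophil and lymphocyte counts among the recipient data. A trigger worded only as an increase gives these no rule.

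The threshold also cannot be computed from what the plan provides. The analysis plan produces no s.d. of any kind. The text schedules a blood count and metabolic panel both at the screening evaluation (Day -7 to 0) and on Day 0, so the baseline could be either value, and one or two values give no usable within-patient s.d.

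Safety is a primary objective, the analysis is descriptive and there are 10 recipients. AE proportions are therefore a main safety output, and one recipient classified differently moves a proportion by 1/10, or 10 percentage points.

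**Working it through.** The plan gives no flag rate for this rule, so there is no stated figure to reproduce. The check asks how the trigger behaves under each plausible meaning of s.d.

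**Inputs**

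- Threshold: a rise of 2 s.d. (the sentence itself).
- Post-baseline draws: 4 (Table 2: days 1, 3, 7, 14) or 8 (text: daily on days 1 to 7, plus day 14).
- Recipients: 10.
- Analytes: not stated. Assumed 20, range 10 to 25.
- Also assumed: normal variation and no true change from baseline.

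**Chance that one later value is flagged**

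- Reading A, s.d. of the change (or an error-free baseline): 1 − Φ(2) = 2.28%.
- Reading B, within-patient s.d. with a single noisy baseline. The difference of two values has s.d. √2 times as large, so 1 − Φ(2/√2) = 1 − Φ(1.414) = 7.86%.
- Reading C, between-patient s.d. with within-patient correlation ρ: 1 − Φ(2/√(2(1 − ρ))). This is 2.28% at ρ = 0.5, 0.49% at 0.7 and 0.08% at 0.8.

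**Expected chance flags = analytes × draws × probability.** With 20 analytes there are 20 × 4 = 80 or 20 × 8 = 160 comparisons per recipient.

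| Reading | Per recipient, 4 draws | Per recipient, 8 draws | All 10 recipients |
|---|---|---|---|
| A | 1.8 | 3.6 | 18 to 36 |
| B | 6.3 | 12.6 | 63 to 126 |
| C, ρ = 0.8 | 0.06 | 0.13 | 0.6 to 1.3 |

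Over 10 to 25 analytes and 4 or 8 draws, the totals for 10 recipients run from 9 to 46 (A), 31 to 157 (B) and 0.3 to 1.6 (C, ρ = 0.8). These are expected counts, so they do not require the analytes to be independent.

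**Falls.** If the true value drops by 2 s.d., the observed value must still come out 2 s.d. above baseline to be flagged. The probability is 1 − Φ(4) = 0.003% under A and 1 − Φ(4/√2) = 0.23% under B. Taken alone, the trigger does not detect falls.

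**Making the same rule two-sided.** The chance rate doubles, to 4.55% (A) or 15.73% (B) per test, while a true 2 s.d. fall is caught about 50% of the time. Adding a direction without replacing the s.d. mends one defect and worsens the other.

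**The case against.** A reader might infer that every harmful fall is missed. The documents do not support that. The sentence says if, not only if, and no clause gives it precedence over the general AE definition, under which an abnormal low value can be an AE. Documentation is left to the clinician. Blood dyscrasias appear among the examples of important medical events in the SAE definition. Halting items 5 and 6 work by judgment and are not tied to a direction. All of this stands. What remains is that a rise has a rule and a fall has only discretion.

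A reader might also infer that the laboratory safety data are corrupted, or that noise could stop the study. Neither follows. The values are collected whether or not they become AEs, and the planned minimum shows falls. A chance rise that needs no escalation of treatment is not Grade 3 on the protocol's scale. Halting item 4 refers to laboratory toxicity rather than laboratory AEs and also requires association with the product, so it does not run through the 2 s.d. rule.

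Finally, it is tempting to quote only the 7.9% per test. That holds under one reading of an undefined term; others give 2.3% or 0.08%. The rule also speaks of abnormalities, so if a rise within the normal range does not count, all the flag counts above are too high. The sound conclusion is that the flag rate is indeterminate, not that it is high.

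**Conclusion.** The rule is wrong as written, on two counts. First, the only numerical trigger covers rises, so falls in scheduled safety tests have no reporting trigger; this conflicts with the direction-neutral AE definition. Second, the s.d. and the baseline are undefined. Expected chance flags per recipient range from about 0.06 to about 13 across the readings, so the laboratory AE count cannot be reproduced.

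The range rests on 20 assumed analytes, normal variation and stable true values; acutely ill patients will also have real changes. The consequence is confined to laboratory AE counts and possibly the Grade 3 or higher AE proportion. In a descriptive single-group pilot no test or error rate is affected.

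Separately, halting item 4 depends on a laboratory grade for a given parameter, while the only severity scale contains no laboratory limits. A grade can be inferred from the treatment an event required, but the protocol does not say that this is what item 4 means.

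**What to change.** Replace the sentence with a definition such as: *A laboratory abnormality is an AE when it worsens from the Day 0 value, in either direction, by at least one grade on [a published numeric laboratory grading scale, named by the sponsor].* For any scheduled analyte the scale does not cover, state the reporting limit and its direction. Align the text with the general AE definition and say how clinician judgment adds to the rule. In the analysis section, add a table of worst post-baseline grade against baseline grade for each analyte.

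For halting item 4, the sponsor should reconcile its wording with the severity scale, so that the meaning of a laboratory grade there is explicit.

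The cost is protocol wording and one standard table. The small downside is grading in both directions for 10 recipients, with more laboratory AEs likely to be recorded in severely ill patients. The shift table helps the reader judge these, because it shows each recipient's starting grade.
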